#### 2. Objectives of the study

This study aimed to recruit a group of patients with irritable bowel syndrome (IBS) to use the Ruisenan portable auricular conic stimulator. (1) To observe the improvement of symptoms in patients with IBS; (2) To analyze the changes of gut microbiota in patients with irritable bowel syndrome; (3) verify whether the level of intestinal inflammation is reduced and find metabolic markers in the gut.

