#### 3. Study design

This was a randomized, double-blind study without placebo. Forty patients with physician-diagnosed IBS-D were recruited. The recruited patients were randomly assigned to undergo either real tVNS (transcutaneous vagus nerve stimulation) or sham TVNS (using the same device but without vagus nerve stimulation) at different times.

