#### 4.Selection of subjects

#### 1. Eligibility Criteria

1.1 Patients with colorectal cancer were excluded by colonoscopy within two years, and the clinical manifestations were diarrhea predominant irritable bowel syndrome, which met the Rome IV diagnostic criteria. That is, recurrent abdominal pain or discomfort, occurring at least 3 days per month in the past 3 months, and meeting the following two or more points:

- (1) Improvement after defecation;
- (2) the change of the frequency of defecation;
- (3) The onset of the disease accompanied by changes in stool character (appearance).

\* Symptoms have been present for at least 6 months before diagnosis, and symptoms have met the above criteria for the past 3 months

\* Discomfort refers to non-painful discomfort. For pathophysiological studies and clinical trials, the frequency of pain/discomfort used for screening assessment is at least two days per week when selecting subjects for research.

1.2 Patients with diarrhea and irritable bowel were mainly selected for enrollment.

1.3 The enrolled patients with IBS were between 18 and 65 years of age and had a normal electrocardiogram before enrollment.

1.4 Subjects were excluded from the study if they did not meet the requirements by having them fill out the questionnaire to assess the health status of the intestinal health-related questionnaire.

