#### 5. Estimation of sample size

Forty patients with diarrhea-predominant irritable bowel syndrome

[figure not shown]

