#### **6.Study PROCEDURE**

Stool samples were collected from patients with diarrhea-type irritable bowel syndrome. The auricular concha-stimulator was used for 3 hours per day with a pulse width of 200µs and a frequency of 30Hz. Each patient was randomly selected for true stimulation or sham stimulation every 4 weeks for 8 weeks, resulting in a total of 4 groups, namely, true-true, true-false, false-true, and false-false (FIG. 2). Stool samples were collected on day 0, day 28 and day 56. Stool samples were collected two weeks after the end of the treatment. Patients completed questionnaires on day 0 and every other 7 days thereafter, for a total of 11 questionnaire collections (Figure 1); the questionnaires are shown in Table 2.

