#### 9. Data collection and statistical analysis

The degree of pain, the frequency of diarrhea, and the degree of abdominal distension were used to evaluate the changes in the patient's irritable bowel status. The degree of pain refers to the use of psychometric practices to evaluate the patient's subjective feeling, which is also considered to be the main factor to evaluate the poor health-related quality of life (HRQL). The severity of irritable bowel syndrome was measured according to the Gastrointestinal Symptom Rating Scale for Irritable Bowel Syndrome (GSRS-IBS). On the GSRS-IBS scale, a score of 1 to 3 is defined as mild symptoms, a score of 4 or 5 as more severe, and a score of 6 or 7 as extremely severe.

Two-way analysis of variance (ANOVA) was used for statistical analysis. Two-sided t test was used for pairwise comparison, and p value was corrected for multiple comparisons. Kruskal-Wallis test was used for multiple group comparison. Spearman correlation analysis was used to determine the correlation between gut microbiota alterations and biological and pathological parameters related to constipation, with p values corrected by Benjamini-Hochberg method (Benjamini and Hochberg, 1995). A False Discovery Rate (FDR) threshold of 0.1 was used to consider the p value statistically significant. p < 0.05 or p < 0.01 was considered statistically significant. All rule plots were generated using GraphPad Prism version 8.0 (La Jolla, CA, United States). All statistical analyses were performed using GraphPad prismore and R(version 4.1.2,https://www.r-project.org/)

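### The plan's one microbiota correlation is aimed at constipation parameters, although the trial studies diarrhoea-predominant IBS

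*Combined protocol and SAP*

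**What the plan says.** Section 9 (Data collection and statistical analysis) specifies one association analysis. Spearman correlation relates gut microbiota alterations to "biological and pathological parameters related to constipation", with p values corrected by Benjamini-Hochberg. The parameters are not listed.

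The population is described differently throughout:

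- Section 3: "Forty patients with physician-diagnosed IBS-D were recruited".
- Section 4, criterion 1.1: "the clinical manifestations were diarrhea predominant irritable bowel syndrome". Criterion 1.2 adds that diarrhoea patients were mainly selected.
- Section 5: "Forty patients with diarrhea-predominant irritable bowel syndrome".
- Section 6: the stool samples come from patients with the diarrhoea type.

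Section 9 also names its own symptom measures: "The degree of pain, the frequency of diarrhea, and the degree of abdominal distension were used to evaluate the changes". It measures severity on the GSRS-IBS. Objective 2 in section 2 reads "To analyze the changes of gut microbiota in patients with irritable bowel syndrome".

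**The concern.** The target of the correlation does not match the disease the trial enrols or the measures by which the same section judges change. An analyst following the text would correlate microbiota with constipation variables in patients selected for diarrhoea. An analyst who recognised the slip would have to choose replacement variables without guidance, possibly after seeing the data. Because the parameters are unlisted, the family of tests for the Benjamini-Hochberg correction is also undefined. At stake is the one planned analysis that could show whether microbiota changes go along with the condition being treated.

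**Working it through.** This is a consistency check of the text. Section 5 gives only the number of patients, and no figure in the plan bears on this point, so there is nothing to reproduce.

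**1. Target against population.** The target in section 9 is constipation. The population in sections 3, 4 (criterion 1.1), 5 and 6 is diarrhoea-predominant IBS. The qualifier in criterion 1.2 might admit a few other patients, but it does not make constipation the condition studied.

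**2. Target against the section's own measures.** Section 9 names pain, diarrhoea frequency and abdominal distension, plus GSRS-IBS severity. None of the three named symptoms is constipation.

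**3. Is it corrected elsewhere?** In the text available, constipation otherwise appears in the account of the earlier pilot study in section 1, where 5 of 9 evaluable patients had the constipation type, and in GSRS-IBS item 5 in Table 1. Neither defines a constipation outcome for this trial.

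**4. Does another analysis fill the gap?** Section 2 and the text under Figure 2 in section 6 plan to describe changes in microbiota and metabolites. The ANOVA, t test and Kruskal-Wallis test in section 9 are group comparisons. None relates microbiota to clinical or biological parameters within patients, so the Spearman sentence stands alone.

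**5. Which days could a corrected analysis use?** Two things are needed: a stool day on which both accounts in section 6 agree, and a questionnaire on the same day.

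- *Stool, first account:* "Stool samples were collected on day 0, day 28 and day 56", then a collection two weeks after treatment ends, that is 56 + 14 = day 70.
- *Stool, text under Figure 2:* days 0, 28, 56, 63 and 70.
- *Agreed days after baseline:* 28, 56 and 70. Day 63 appears only in the second account.
- *Questionnaires:* 11 collections from day 0 at 7-day spacing run to 7 × (11 − 1) = day 70. They include days 28, 56 and 70.

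The GSRS-IBS asks about the past 2 weeks (Table 1). The recall windows are:

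| Day | Window | Where it falls |
|---|---|---|
| 28 | 14–28 | inside the first 4-week period |
| 56 | 42–56 | inside the second 4-week period |
| 70 | 56–70 | wholly after treatment |
| 63 | 49–63 | straddles the end of treatment |

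Days 28, 56 and 70 therefore each give a same-day pair with a clean recall window. With one pair per patient per day, there are at most 40 pairs on each day.

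**The case against.** The strongest reply is that this is one wrong word in an exploratory analysis, that any reader would see it as a carry-over, and that no objective in section 2 calls for a correlation between microbiota and symptoms. Most of that is fair, and it limits the weight of the point. It does not remove it. The word stands in the current statistical section, and swapping in another word would still leave the parameters unlisted.

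Four stronger readings are tempting, and the documents do not support them.

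- *That the plan's link between microbiota and symptoms is lost.* Section 9 speaks of biological and pathological parameters, not symptoms. The plan does not establish that symptoms were to be the correlates.
- *That the loss can be counted in questionnaire items.* A reader might note that GSRS-IBS items 5 and 8 concern constipation or dry stools and work out what share of the 13 items lies outside the target. That assumes GSRS-IBS items are the correlates, which section 9 never says. Nor is constipation touched only by those two items: item 10 (incomplete emptying) and item 32 of the second questionnaire (fear of not being able to defecate properly) can also be read that way.
- *That the microbiota or efficacy results as a whole are compromised.* The group comparisons do not depend on this sentence.
- *That the correlation must be adjusted for true or sham allocation.* Pooling the arms can produce correlation through a shared treatment difference, but adjusting changes the question to association within arms. How much it matters depends on effect sizes the documents do not give. It is a separate design choice.

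One practical objection stands. Section 9 does not say which recorded item represents each named measure. GSRS-IBS item 6 rates how troublesome diarrhoea is rather than counting stools, both bloating (item 3) and swelling (item 13) could represent distension, and no GSRS-IBS total score is defined.

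**Conclusion.** The concern holds. Section 9 aims its only microbiota association analysis at a condition the trial does not study, and nothing in the available text corrects it. Followed as written, the analysis would not address diarrhoea-predominant IBS. The effect is limited to this correlation; the comparisons for objectives 1 and 2 are untouched. It should be corrected before the correlation is run, but it does not threaten the trial's main comparisons.

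That the word is a carry-over is an inference, and the conclusion does not depend on it. No significance level, power, effect size or sample size enters the argument. The choice of days assumes that the 11 questionnaires are 7 days apart and that the collection two weeks after treatment falls on day 70.

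**What to change.** In section 9, replace the constipation target with: *parameters related to diarrhoea-predominant IBS, namely change from day 0 in pain, diarrhoea frequency, abdominal distension and GSRS-IBS severity, as already named in this section.* Then add:

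- The correlation is run separately at days 28, 56 and 70, with one pair per patient per day.
- Benjamini-Hochberg is applied within each day, across all taxa and the listed parameters.

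The sponsor should state which recorded item or score stands for each parameter. Any biological marker that is also intended should be named in the list beforehand, since an open-ended entry would leave the family of tests undefined again.

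The cost is wording and minor analysis work. The stool samples and questionnaires on these days are already planned. If diarrhoea frequency is not recorded as a count, the sponsor should say which existing item serves in its place.

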

[28] Mion, F., et al., Transcutaneous auricular vagus nerve stimulation for the treatment of irritable bowel syndrome: a pilot, open-label study. Bioelectronics in Medicine, 2020. 3(1): p. 5-12.

| Table 1. Gastrointestinal Symptom Rating Scale for Irritable Bowel Syndrome (GSRS-IBS). |           |           |           |           |           | -IBS).    |           |
|---|-----------|-----------|-----------|-----------|-----------|-----------|-----------|
| The   | No        | Slight    | Mild      | Moderate  | Moderate  | Severe    | Very      |
| following   | discomfor | discomfor | discomfor | discomfor | to severe | discomfor | severe    |
| questions   | t at all  | t         | t         | t         | discomfor | t         | discomfor |
| relate to the   |           |           |           |           | t         |           | t         |
| symptoms  | 1         | 2         | 3         | 4         | 5         | 6         | 7         |
| of irritable  |           |           |           |           |           |           |           |
| bowel   |           |           |           |           |           |           |           |
| syndrome.   |           |           |           |           |           |           |           |
| The severity  |           |           |           |           |           |           |           |
| or intensity  |           |           |           |           |           |           |           |
| of the  |           |           |           |           |           |           |           |
| following   |           |           |           |           |           |           |           |
| symptoms  |           |           |           |           |           |           |           |
| during the  |           |           |           |           |           |           |           |
| past 2 weeks  |           |           |           |           |           |           |           |
| 1. Are you  |           |           |           |           |           |           |           |
| bothered by   |           |           |           |           |           |           |           |
| abdominal   |           |           |           |           |           |           |           |
| pain?   |           |           |           |           |           |           |           |
| 2. Have you   |           |           |           |           |           |           |           |

Table 1. Gastrointestinal Symptom Rating Scale for Irritable Bowel Syndrome (GSRS-IBS).

|               | 1 | [ | [ | [ | r | r | 1 |
|---------------|---|---|---|---|---|---|---|
| ever felt     |   |   |   |   |   |   |   |
| pain or       |   |   |   |   |   |   |   |
| discomfort    |   |   |   |   |   |   |   |
| in your       |   |   |   |   |   |   |   |
| abdomen       |   |   |   |   |   |   |   |
| that relieved |   |   |   |   |   |   |   |
| with bowel    |   |   |   |   |   |   |   |
| movements?    |   |   |   |   |   |   |   |
| 3. Have you   |   |   |   |   |   |   |   |
| been          |   |   |   |   |   |   |   |
| bothered by   |   |   |   |   |   |   |   |
| feelings of   |   |   |   |   |   |   |   |
| bloating?     |   |   |   |   |   |   |   |
| 4. Are you    |   |   |   |   |   |   |   |
| bothered by   |   |   |   |   |   |   |   |
| gas?          |   |   |   |   |   |   |   |
| 5. Do you     |   |   |   |   |   |   |   |
| suffer from   |   |   |   |   |   |   |   |
| constipation  |   |   |   |   |   |   |   |
| (difficulty   |   |   |   |   |   |   |   |
| defecating)?  |   |   |   |   |   |   |   |
| 6. Do you     |   |   |   |   |   |   |   |
| suffer from   |   |   |   |   |   |   |   |
| diarrhea      |   |   |   |   |   |   |   |
| (frequent     |   |   |   |   |   |   |   |
| bowel         |   |   |   |   |   |   |   |
| movements)    |   |   |   |   |   |   |   |
| ?             |   |   |   |   |   |   |   |
| 7. Do you     |   |   |   |   |   |   |   |
| have trouble  |   |   |   |   |   |   |   |
| having loose  |   |   |   |   |   |   |   |
| bowel         |   |   |   |   |   |   |   |
| movements?    |   |   |   |   |   |   |   |
| 8. Do you     |   |   |   |   |   |   |   |
| have          |   |   |   |   |   |   |   |
| difficulty    |   |   |   |   |   |   |   |
| bowel         |   |   |   |   |   |   |   |
| movements     |   |   |   |   |   |   |   |
| because       |   |   |   |   |   |   |   |
| your stools   |   |   |   |   |   |   |   |
| are dry?      |   |   |   |   |   |   |   |
| 9. Have you   |   |   |   |   |   |   |   |
| ever been     |   |   |   |   |   |   |   |
| bothered by   |   |   |   |   |   |   |   |
| J             | 1 | 1 | 1 | 1 | 1 | 1 |   |

| the urgent      |  |  |  |  |
|-----------------|--|--|--|--|
| need to         |  |  |  |  |
| defecate (the   |  |  |  |  |
| need to go to   |  |  |  |  |
| the toilet to   |  |  |  |  |
|                 |  |  |  |  |
| defecate)?      |  |  |  |  |
| 10. Do you      |  |  |  |  |
| have the        |  |  |  |  |
| feeling that    |  |  |  |  |
| your bowel      |  |  |  |  |
| movements       |  |  |  |  |
| are             |  |  |  |  |
| incomplete?     |  |  |  |  |
| 11. Do you      |  |  |  |  |
| feel full       |  |  |  |  |
| soon after      |  |  |  |  |
| you start a     |  |  |  |  |
| meal?           |  |  |  |  |
| 12. Do you      |  |  |  |  |
| still feel full |  |  |  |  |
| long after      |  |  |  |  |
| you stop        |  |  |  |  |
| eating?         |  |  |  |  |
| 13. Do you      |  |  |  |  |
| have            |  |  |  |  |
| significant     |  |  |  |  |
| abdominal       |  |  |  |  |
| swelling?       |  |  |  |  |

| The following questions relate to the         | no | A little | More | Quite a lot | Totally so |
|---|----|----------|------|-------------|------------|
| symptoms of irritable bowel syndrome.         |    | bit      |      |             | 5          |
| The severity or intensity of the following    | 0  | 1        | 2    | 3           | 4          |
| symptoms during the past week                 | 0  | -        | -    |             |            |
| 1. I feel helpless because of my bowel        |    |          |      |             |            |
| movements                                     |    |          |      |             |            |
| 2. The smell caused by my stool makes         |    |          |      |             |            |
| me feel embarrassed                           |    |          |      |             |            |
| 3. I worry about how much time I spend        |    |          |      |             |            |
| in the bathroom                               |    |          |      |             |            |
| 4. Because of my defecation problems, I       |    |          |      |             |            |
| feel vulnerable to other diseases             |    |          |      |             |            |
| 5. I feel like I'm putting on weight          |    |          |      |             |            |
| because of my bowel problems                  |    |          |      |             |            |
|   |    |          |      |             |            |
| 6. I feel unable to organize my life          |    |          |      |             |            |
| because of my bowel problems                  |    |          |      |             |            |
| 7. I feel unhappy with my life because of     |    |          |      |             |            |
| my bowel problems                             |    |          |      |             |            |
| 8. I feel uncomfortable whenever I talk       |    |          |      |             |            |
| about my bowel problems                       |    |          |      |             |            |
| 9. I feel frustrated about having problems    |    |          |      |             |            |
| with my bowel movements                       |    |          |      |             |            |
| 10. I feel disconnected from those around     |    |          |      |             |            |
| me because of my bowel problems               |    |          | -    |             |            |
| 11. I have to watch how much I eat            |    |          |      |             |            |
| because of my bowel problems                  |    |          |      |             |            |
| 12. My sex life is not working because of     |    |          |      |             |            |
| my bowel movements                            |    |          |      |             |            |
| 13. I feel angry about my bowel               |    |          |      |             |            |
| movements                                     |    |          |      |             |            |
| 14.1. I feel prone to irritating others       |    |          |      |             |            |
| because of my bowel problems                  |    |          |      |             |            |
| 15. I'm worried that my bowel problems        |    |          |      |             |            |
| are going to get worse                        |    |          |      |             |            |
| 16. I feel irritable and irritable because of |    |          |      |             |            |
| my bowel movements                            |    |          |      |             |            |
| 17. I'm worried that people think I'm         |    |          |      |             |            |
| exaggerating my bowel problems                |    |          |      |             |            |
| 18. Do I feel like I can't get anything       |    |          |      |             |            |
| done because of my bowel movements            |    |          |      |             |            |
| 19. I have to avoid stressful situations      |    |          |      |             | 1          |
| because of my bowel problems                  |    |          |      |             |            |
| 20. My bowel problems have reduced my         |    |          |      | 1           | 1          |
| libido  |    |          |      |             |            |

| 22. Because of my defecation problems, I  |   | - | 1 |      | 1 |
|---|---|---|---|------|---|
| have to avoid strenuous exerciseImage: Image: I | 21. My bowel problems limit what I wear       |   |   |      |   |
| 23. Because of my defecation problems, I  | 22. Because of my defecation problems, I      |   |   |      |   |
| have to watch what kind of food I eat   | have to avoid strenuous exercise              |   |   |      |   |
| 24. I have trouble getting along with
unfamiliar people because of my bowel
movements       Image: Constraint of the second          | 23. Because of my defecation problems, I      |   |   |      |   |
| unfamiliar people because of my bowel
movementsImage: Constraint of the second  | have to watch what kind of food I eat         |   |   |      |   |
| movementsImage: constraint of the second | 24. I have trouble getting along with         |   |   |      |   |
| 25. I feel slow to respond because of my
bowel movements26. I feel unclean because of my
defecation problems27 It is difficult for me to travel long
distances because I have problems with
  | unfamiliar people because of my bowel         |   |   |      |   |
| bowel movementsImage: Constraint of the second  | movements                                     |   |   |      |   |
| 26. I feel unclean because of my       26. I feel unclean because of my         defecation problems       27 It is difficult for me to travel long         distances because I have problems with       27 It is difficult for me to travel long         distances because I have problems with       28. I feel frustrated that I can't eat what I         want because of my defecation problems       29. Being close to the bathroom is         necessary because of my defecation       29. Being close to the bathroom is         necessary because of my defecation       20. My daily life revolves around my         bowel problems.       20. My daily life revolves around my         bowel problems.       23. I worry about not being able to         control my bowel movements       23. I'm afraid I won't be able to defecate         properly       33. My bowel problems are affecting my         relationships with those closest to me       23. If eel like no one understands my   | 25. I feel slow to respond because of my      |   |   |      |   |
| defecation problemsImage: constraint of the second sec | bowel movements                               |   |   |      |   |
| 27 It is difficult for me to travel long       27 It is difficult for me to travel long         distances because I have problems with       my bowel movements         28. I feel frustrated that I can't eat what I       28. I feel frustrated that I can't eat what I         want because of my defecation problems       29. Being close to the bathroom is         necessary because of my defecation       29. Being close to the bathroom is         necessary because of my defecation       20. My daily life revolves around my         bowel problems.       20. My daily life revolves around my         30. My daily life revolves around my       20. My daily life revolves around my         bowel problems.       23. I'm afraid I won't be able to defecate         groperly       33. My bowel problems are affecting my         relationships with those closest to me       23. I'feel like no one understands my  | 26. I feel unclean because of my              |   |   |      |   |
| distances because I have problems with
my bowel movementsImage: Constraint of the second sec  | defecation problems                           |   |   |      |   |
| my bowel movementsImage: constraint of the set of th | 27 It is difficult for me to travel long      |   |   |      |   |
| 28. I feel frustrated that I can't eat what I
want because of my defecation problems29. Being close to the bathroom is
necessary because of my defecation
problems30. My daily life revolves around my
bowel problems.31. I worry about not being able to
control my bowel movements32. I'm afraid I won't be able to defecate
properly33. My bowel problems are affecting my
relationships with those closest to me34. I feel like no one understands my  | distances because I have problems with        |   |   |      |   |
| want because of my defecation problemsImage: Constraint of the bathroom is necessary because of my defecation problemsImage: Constraint of the bathroom is necessary because of my defecation problemsImage: Constraint of the bathroom is necessary because of my defecation problemsImage: Constraint of the bathroom is necessary because of my defecation problemsImage: Constraint of the bathroom is necessary because of my defecation problemsImage: Constraint of the bathroom is necessary because of my defecation problemsImage: Constraint of the bathroom is necessary because of my defecation problemsImage: Constraint of the bathroom is necessary because around my bowel problems are affecting my relationships with those closest to meImage: Constraint of the bathroom is necessary because around my bathroom is necessary because are affecting my relationships with those closest to meImage: Constraint of the bathroom is necessary because are affecting my relationships with those closest to meImage: Constraint of the bathroom is necessary because are affecting my relationships with those closest to meImage: Constraint of the bathroom is necessary because are affecting my relationships with those closest to meImage: Constraint of the bathroom is necessary because are affecting my relationships with those closest to meImage: Constraint of the bathroom is necessary because are affecting my relationships with those closest to meImage: Constraint of the bathroom is necessary because are affecting my relationships with those closest to meImage: Constraint of the bathroom is necessary because are affecting my relationships with those closest to meImage: Constraint of the bathroom is necessary because are affecting my relationships with those closest to meImage: Constraint of the bathroom is necessary because are affecting my relationships with the closest to  | my bowel movements                            |   |   |      |   |
| 29. Being close to the bathroom is         necessary because of my defecation         problems         30. My daily life revolves around my         bowel problems.         31. I worry about not being able to         control my bowel movements         32. I'm afraid I won't be able to defecate         properly         33. My bowel problems are affecting my         relationships with those closest to me         34. I feel like no one understands my  | 28. I feel frustrated that I can't eat what I |   |   |      |   |
| necessary because of my defecation
problemsImage: Constraint of the second sec  | want because of my defecation problems        |   |   |      |   |
| problemsImage: control my bowel problems.Image: control my bowel movements31. I worry about not being able to control my bowel movementsImage: control my bowel movements32. I'm afraid I won't be able to defecate properlyImage: control my bowel problems are affecting my relationships with those closest to me34. I feel like no one understands myImage: control my bowel my bo   | 29. Being close to the bathroom is            |   |   |      |   |
| 30. My daily life revolves around my         bowel problems.         31. I worry about not being able to         control my bowel movements         32. I'm afraid I won't be able to defecate         properly         33. My bowel problems are affecting my         relationships with those closest to me         34. I feel like no one understands my   | necessary because of my defecation            |   |   |      |   |
| bowel problems.Image: Control my bowel movementsImage: Control my bowel movements32. I'm afraid I won't be able to defecate
properlyImage: Control my bowel movementsImage: Control my bowel movements33. My bowel problems are affecting my
relationships with those closest to meImage: Control my bowel movementsImage: Control my bowel movements34. I feel like no one understands myImage: Control my bowel movementsImage: Control my bowel movements  | problems                                      |   |   |      |   |
| 31. I worry about not being able to   | 30. My daily life revolves around my          |   |   |      |   |
| control my bowel movementsImage: Control my bowel movements32. I'm afraid I won't be able to defecate
properlyImage: Control my bowel problems are affecting my
relationships with those closest to me33. My bowel problems are affecting my
relationships with those closest to meImage: Control my bowel problems are affecting my
relationships with those closest to me34. I feel like no one understands myImage: Control my bowel problems are affecting my
relationships with those closest to me   | bowel problems.                               |   |   |      |   |
| 32. I'm afraid I won't be able to defecate  | 31. I worry about not being able to           |   |   |      |   |
| properlyImage: Constraint of the second  | control my bowel movements                    |   |   |      |   |
| 33. My bowel problems are affecting my relationships with those closest to me       34. I feel like no one understands my   | 32. I'm afraid I won't be able to defecate    |   |   |      |   |
| relationships with those closest to me 34. I feel like no one understands my  | properly                                      |   |   |      |   |
| 34. I feel like no one understands my   | 33. My bowel problems are affecting my        |   |   | 
 |   |
|   | relationships with those closest to me        |   |   |      |   |
| bowel movements   | 34. I feel like no one understands my         |   |   |      |   |
|   | bowel movements                               |   |   |      |   |

